5. TREATMENT OF SUBJECTS

5.1. Study Medications

5.1.1. Ibrutinib

5.1.1.1. Formulation/Packaging/Storage

Ibrutinib capsules are provided as a hard gelatin capsule containing 70 mg and 140 mg of ibrutinib. All formulation excipients are compendial and are commonly used in oral formulations. Refer to the ibrutinib IB for a list of excipients. 70 mg capsules will only be used for subjects who have dose reductions that require a dose of 70 mg and will not be used to constitute a dose larger than 70 mg (eg, 2 x 70 mg capsules to give 140 mg).

The ibrutinib capsules will be packaged in opaque high-density polyethylene plastic bottles with labels bearing the appropriate label text as required by governing regulatory agencies. All study drug will be dispensed in child-resistant packaging.

Study drug labels will contain information to meet the applicable regulatory requirements.

5.1.1.2. Dose and Administration

Ibrutinib 420 mg (3 x 140-mg capsules) is administered orally once daily. It is expected that many subjects commencing therapy for cGVHD will require anti-fungal prophylaxis. Please see Section 6.2.1 for dose modification guidelines with concomitant use of CYP3A inhibitors.

The capsules are to be taken around the same time each day with 8 ounces (approximately 240 mL) of water. The capsules should be swallowed intact and subjects should not attempt to open capsules or dissolve them in water. The use of strong CYP3A inhibitors/inducers (other

than those specifically permitted on study), and grapefruit and Seville oranges should be avoided for the duration of the study ([Appendix C](#)).

If a dose is not taken at the scheduled time, it can be taken as soon as possible on the same day with a return to the normal schedule the following day. The subject should not take extra capsules to make up the missed dose.

The first dose will be delivered in the clinic on Day 1, after which subsequent dosing is typically on an outpatient basis. Ibrutinib will be dispensed to subjects in bottles at each visit. Study drug may not be shipped to the subject without approval from PCYC and may not be dispensed to anyone other than the subject. Unused ibrutinib dispensed during previous visits must be returned to the site and drug accountability records ([Section 12.5](#)) updated at each visit. Returned capsules must not be redispensed to anyone.

5.1.1.3. Overdose

There is no specific experience in the management of ibrutinib overdose in patients. No maximum tolerated dose (MTD) was reached in the Phase 1 study in which subjects received up to 12.5 mg/kg/day (1,400 mg/day). Healthy subjects were exposed up to single dose of 1680 mg. One healthy subject experienced reversible Grade 4 hepatic enzyme increases (AST and ALT) after a dose of 1680 mg. Subjects who ingest more than the recommended dosage should be closely monitored and given appropriate supportive treatment.

Refer to [Section 11.3](#) for further information regarding special reporting situations as a result of overdose.

5.1.1.4. Dose Modification for Non-Cardiac Adverse Reactions

The dose of study drug must be modified according to the dose modification guidance in [Table 1](#) and [Table 2](#) if any of the following non-cardiac toxicities occur:

- Grade 4 neutropenia (ANC <500/ μ L) for more than 7 days. See [Section 6.1](#) for instructions regarding the use of growth factor support.
- Grade 3 thrombocytopenia (platelets <50,000/ μ L) in the presence of clinically significant bleeding events.
- Grade 4 thrombocytopenia (platelets <25,000/ μ L).
- Grade 3 or 4 nausea, vomiting, or diarrhea if persistent, despite optimal anti-emetic and/or anti-diarrheal therapy.
- Any other Grade 4 or unmanageable Grade 3 non-cardiac toxicity

Adverse events that are considered related to concomitant high dose corticosteroids (e.g. hyperglycemia, insomnia) do not require dose modification or holding of ibrutinib.

If the dose of ibrutinib is reduced, at the investigator's discretion, the dose of ibrutinib may be re-escalated after 4 weeks of a dose reduction in the absence of a recurrence of the toxicity that led to the reduction. Dose changes must be recorded in the CRF.

Table 1. Ibrutinib Dose Modifications

Occurrence	Action to be Taken
First	Withhold study drug until recovery to Grade ≤ 1 or baseline; may restart at original dose level
Second	Withhold study drug until recovery to Grade ≤ 1 or baseline; may restart at 1 dose level lower (i.e., 280 mg/day for 420 mg/day dose)
Third	Withhold study drug until recovery to Grade ≤ 1 or baseline; may restart at 1 dose level lower (i.e., 140 mg/day for 420 mg/day dose; 280 mg/day)
Fourth	Discontinue study drug

Table 2. Ibrutinib Dose Reduction Levels

Starting Dose Level	140 mg	280 mg	420 mg
Dose Reduction Level 1	70 mg	140 mg	280 mg
Dose Reduction Level 2	Discontinue	70 mg	140 mg
Dose Reduction Level 3	NA	Discontinue	Discontinue

For required dose modification for hepatic impairment refer to [Section 5.1.1.5](#) and for concomitant treatment with CYP3A inhibitors refer to [Section 5.1.1.6](#).

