5.1.1.5. Dose Modification for Cardiac Toxicity

The dose of study drug must be modified for cardiac toxicity according to the guidance in Table 3:

Table 3: Dose Modification Guidance for Cardiac Toxicity

Adverse Reaction	Occurrence	Dose Modification After Recovery Starting Dose=420mg	Dose Modification After Recovery Starting Dose=280mg	Dose Modification After Recovery Starting Dose=140mg
Grade 2 cardiac failure ¹	First	Restart at 280 mg	Restart at 140 mg	Restart at 70 mg
	Second	Restart at 140 mg	Restart at 70 mg	Discontinue Drug
	Third	Discontinue Drug	Discontinue Drug	N/A
Grade 3 cardiac arrhythmias ^{1,2}	First	Restart at 280mg	Restart at 140 mg	Restart at 70 mg
	Second	Discontinue Drug	Discontinue Drug	Discontinue Drug
Grade 3 or 4 cardiac failure Grade 4 cardiac arrhythmias	First	Discontinue Drug	Discontinue Drug	Discontinue Drug

¹Evaluate the risk-benefit before resuming ibrutinib treatment

²If clinically indicated, the use of anticoagulants or antiplatelet agents may be considered for thromboprophylaxis of atrial fibrillation.

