5.1.1.6. Dose Modification for Hepatic Impairment

Dose modifications for hepatic impairment will depend on total bilirubin level and subsequent changes in bilirubin levels per Table 3 below. If the elevation of bilirubin is due to a non-hepatic cause or Gilbert's Syndrome, then no dose modifications are necessary. Ibrutinib is metabolized in the liver and therefore subjects with clinically significant chronic hepatic impairment at the time of Screening (Child- Pugh class C) are excluded from study participation. Refer to Appendix D for Child-Pugh classification. Please refer to Table 3 for dose modifications due to hepatic impairment. Subjects who develop acute hepatic toxicity with liver enzymes Grade 3 or higher while on study should be managed per standard dose modification guidelines for unmanageable Grade 3 toxicity in Section 5.1.1.4.

Table 4. Dose Modification Guidance for Hepatic Impaired Subjects

Starting Dose Level by Bilirubin Levels	Bili \leq 1.5 x ULN at baseline 420 mg	Bili $>$ 1.5-3 x ULN at baseline 140 mg
On-study Bili \leq 1.5 x ULN	Continue 420 mg	Increase to 420 mg
On-study Bili $>$ 1.5-3 x ULN	Reduce to 140 mg	Continue 140 mg
On-study Bili $>$ 3 x ULN	Hold until Bili $>$ 1.5-3 x ULN, then restart 140 mg When bili level \leq 1.5 x ULN restart at 420mg	Hold until Bili $>$ 1.5-3 x ULN, then restart 140 mg When bili level \leq 1.5 x ULN restart at 420mg

In the event a patient has had a dose reduction due to a non-hepatic toxicity and then develops elevated bilirubin (or vice versa) that requires a dose reduction, the lower of the two dose reductions should be used.

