5.1.1.7. Dose Modification for Concomitant Use of CYP3A Inhibitors

Dose adjustment of ibrutinib secondary to concomitant use of CYP 3A4 inhibitors should follow Table 4. Concomitant use of strong CYP inhibitors is not permitted in subjects with chronic hepatic impairment.

Table 5. Dose Modification Guidance for CYP3A4 Inhibitors

Co-administered Drug	Recommended Ibrutinib Dose for the Duration of the Inhibitor Use
Mild CYP3A4 inhibitors	420 mg once daily. No dose adjustment required.
Moderate CYP3A4 inhibitors	420 mg once daily. No dose adjustment required.
Voriconazole Posaconazole at doses less than or equal to suspension 200 mg BID or delayed-release tablet 300mg QD	280 mg once daily.
Posaconazole at higher doses	140 mg once daily.
Other strong CYP3A4 inhibitors	Avoid concomitant use. If these inhibitors will be used short term (such as anti-infectives for seven days or less), interrupt IMBRUVICA.

After discontinuation of a CYP3A4 inhibitor, resume previous dose of ibrutinib.

If Bili $>$ 1.5 x ULN, avoid and/or discontinue voriconazole, posaconazole, or other strong CYP3A4 inhibitor.

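### An azole added after Day 1 can cancel the ibrutinib reduction that Table 3 requires after a first Grade 3 arrhythmia or Grade 2 cardiac failure

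*Combined protocol and SAP*

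**What the plan says.** Four sets of dosing rules in the combined protocol meet here.

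- **Non-cardiac toxicity (5.1.1.4, Tables 1 and 2).** At the second occurrence the patient "may restart at 1 dose level lower (i.e., 280 mg/day for 420 mg/day dose". At the third, the dose for a 420 mg patient is 140 mg. Table 2 is headed by starting dose: 420 goes to 280 then 140 mg, 280 to 140 then 70 mg, and 140 to 70 mg, each followed by discontinuation.
- **Cardiac toxicity (5.1.1.5, Table 3).** Columns are also headed by starting dose; the first reads "Dose Modification After Recovery Starting Dose=420mg". In that column the entry for a first Grade 2 cardiac failure is "Restart at 280 mg", and a first Grade 3 arrhythmia gives the same dose. The 280 mg column gives 140 mg and the 140 mg column gives 70 mg. Footnote 1 asks for a risk-benefit evaluation before ibrutinib is resumed after either event.
- **CYP3A inhibitors (5.1.1.7, Table 5).** Under the heading "Recommended Ibrutinib Dose for the Duration of the Inhibitor Use", voriconazole and standard-dose posaconazole carry 280 mg, and the row "Posaconazole at higher doses" carries 140 mg. When the inhibitor ends: "After discontinuation of a CYP3A4 inhibitor, resume previous dose of ibrutinib".
- **Combining two reasons for reduction (5.1.1.6).** One rule exists, and it opens "In the event a patient has had a dose reduction due to a non-hepatic toxicity and then develops elevated bilirubin (or vice versa". The lower dose then applies. It does not mention CYP3A inhibitors.

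**The concern.** Table 5 treats 280 mg with voriconazole as the dose that stands in for 420 mg without it. A toxicity step for a patient already on that dose should therefore go below 280 mg. If the restart dose is read from the 420 mg column, it does not: the patient returns to the dose that preceded the cardiac event.

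Every Table 3 column lowers the dose after a first Grade 2 cardiac failure or Grade 3 arrhythmia, and 5.1.1.5 makes modification mandatory. Section 1.2.1.5 lists serious arrhythmias, some fatal, among the risks of ibrutinib. What is at stake is a required safety step that has no effect in one identifiable group: patients who start at 420 mg and add a permitted azole later.

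**Working it through.** This is a table look-up; no sample-size formula is involved.

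**Inputs.** Starting dose 420 mg (5.1.1.2). First-step doses by starting dose: 420 to 280, 280 to 140, 140 to 70 mg (Tables 2 and 3). Table 5 doses: 280 mg (voriconazole or standard-dose posaconazole) and 140 mg (higher-dose posaconazole). Percentage change = restart dose / current dose − 1. The azole is assumed to continue at restart.

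**Step 1, the plan's own case.** No azole, 420 mg starter: 280/420 − 1 = −33%. The plan's intended reduction is reproduced.

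**Step 2, does the column follow the starting dose or the current dose?**
- In Table 3's 420 mg column, the second Grade 2 cardiac failure gives 140 mg. By then the patient is on 280 mg. If the column followed the current dose, the second-occurrence entry in the 280 mg column would apply, which is 70 mg. The column is therefore fixed at the starting dose.
- Table 1's third occurrence gives 140 mg for a 420 mg patient. That is two levels down, so 420 mg there is also the starting dose.
- Table 4 uses the words "Starting Dose Level by Bilirubin Levels" for doses set by baseline bilirubin.

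**Step 3, first Grade 3 arrhythmia or Grade 2 cardiac failure with an azole on board.**

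| Patient | Dose at event | Restart dose | Change |
|---|---|---|---|
| Started 420 mg, no azole | 420 | 280 | −33% |
| Started 420 mg, voriconazole or standard posaconazole added later | 280 | 280 | 280/280 − 1 = 0% |
| Started 280 mg, same azole on board at Day 1 | 280 | 140 | 140/280 − 1 = −50% |
| Started 420 mg, higher-dose posaconazole added later | 140 | column says 280, Table 5 allows 140; lower is 140 | 140/140 − 1 = 0% |

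Rows two and three have the same azole, current dose and event. The restart doses differ two-fold (280/140), and only the azole's start date separates them.

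**Step 4, would the existing combining rule help?** No. It covers toxicity with bilirubin only. Extended to azoles it gives min(280, 280) = 280 mg and min(280, 140) = 140 mg, again no reduction.

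**Step 5, non-cardiac toxicity.** Table 2 read by starting dose gives the same 280 mg at the second occurrence. Table 1's operative instruction, however, is one level lower. Counted from a current 280 mg, that is 140 mg. The text does not settle which applies.

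**Step 6, azole stopped.** Section 5.1.1.7 returns the patient to the previous dose and is silent on a toxicity reduction made meanwhile. The candidates are 420 mg (dose before the azole) and 280 mg (Level 1), a ratio of 420/280 = 1.5.

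**The case against.** The strongest reply is that the plan already provides for azole patients. Table 4 sets baseline doses of only 420 or 140 mg, so a 280 mg starting dose can come only from Table 5, and the 280 mg columns give those patients a true cut. That stands. A reader might infer that toxicity and azole dosing are never connected; they are, for azoles on board at Day 1. The gap is confined to azoles added or stopped later.

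Other stronger readings also fail:

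- **That higher-dose posaconazole doubles the dose, from 140 to 280 mg.** The 420 mg column does say 280 mg, but following it would breach Table 5. The supportable statement is that the tables conflict, and the lower dose is no reduction.
- **That the patient must return to 420 mg when the azole stops.** This is one reading of the previous dose. Table 3 still points to 280 mg for this patient, and nothing says that instruction lapses.
- **That many patients are exposed.** Section 5.1.1.2 expects frequent antifungal prophylaxis in subjects commencing therapy. That describes use around treatment start and gives no rate for later additions.
- **That patients are left unprotected.** Footnote 1 requires a risk-benefit evaluation, and an investigator may choose a lower dose. A second Grade 3 arrhythmia, any Grade 4 arrhythmia and Grade 3 or 4 cardiac failure all mean discontinuation.

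It can also be argued that the plan's only combining policy is non-additive, so stacking reductions is a preference. For bilirubin that is the stated policy. For azoles no policy is stated, and the 280 mg starting-dose column shows that a toxicity step below the azole dose is intended.

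**Conclusion.** The point holds for Table 3. A 420 mg starter with voriconazole or standard-dose posaconazole added after Day 1 is told to restart at an unchanged 280 mg after a first Grade 3 arrhythmia or Grade 2 cardiac failure; a Day 1 azole user restarts at 140 mg. With higher-dose posaconazole, Tables 3 and 5 conflict and the lower dose is again no reduction. The gap in Tables 1 and 2 is real but less firm, because one level lower can be counted from the current dose. Whether a toxicity reduction survives the end of the azole is unstated.

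The conclusion rests on starting dose meaning the dose at study start, which Table 3's second-occurrence entry supports, and on the azole continuing at restart.

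The documents give no frequency. Purely as an assumption, if 10–50% of the 35 patients add an azole after Day 1 and 5–20% of those have a triggering event, between 35 × 0.10 × 0.05 = 0.2 and 35 × 0.50 × 0.20 = 3.5 patients are affected. Alpha and power do not change. This is a dosing-safety correction worth making because a mandatory rule gives no reduction and the remedy is cheap.

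**What to change.** Add to 5.1.1.4, 5.1.1.5 and 5.1.1.7:

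> For a subject receiving voriconazole or posaconazole at the time of the event, use the Table 2 or Table 3 column for the Table 5 dose (280 or 140 mg) if it is lower than the starting dose. For all other subjects, including those started at 140 mg for bilirubin, the column is unchanged. The reduction level reached stays in force when the azole is started or stopped: on voriconazole, Level 1 is 140 mg and Level 2 is 70 mg; after it stops, a 420 mg starter at Level 1 takes 280 mg.

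The limit to azole users matters. If the Table 5 dose chose the column for everyone, a patient started at 140 mg for bilirubin, with no azole, would move to the 420 mg column. That gives 280 mg, held to min(280, 140) = 140 mg by the lower-dose rule in 5.1.1.6: no reduction, where the 140 mg column now gives 70 mg. Keep the bilirubin rule as it is.

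Correct the cross-references at the same time: 5.1.1.4 sends CYP3A questions to 5.1.1.6, now the hepatic section, and 5.1.1.7 and 6.2.1 cite Table 4, now the hepatic table.

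The cost is a short insertion in three subsections and a notice to the site. The 70 mg capsules are already supplied, and no visit or sample size changes. The downside is lower ibrutinib exposure in the few patients affected. On higher-dose posaconazole, discontinuation also comes one step sooner for non-cardiac toxicity and Grade 2 cardiac failure (140, 70, discontinue). The clinical leads should confirm the doses.

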5.1.1.5. Dose Modification for Cardiac Toxicity

The dose of study drug must be modified for cardiac toxicity according to the guidance in Table 3:

Table 3: Dose Modification Guidance for Cardiac Toxicity

Adverse Reaction	Occurrence	Dose Modification After Recovery Starting Dose=420mg	Dose Modification After Recovery Starting Dose=280mg	Dose Modification After Recovery Starting Dose=140mg
Grade 2 cardiac failure ¹	First	Restart at 280 mg	Restart at 140 mg	Restart at 70 mg
	Second	Restart at 140 mg	Restart at 70 mg	Discontinue Drug
	Third	Discontinue Drug	Discontinue Drug	N/A
Grade 3 cardiac arrhythmias ^{1,2}	First	Restart at 280mg	Restart at 140 mg	Restart at 70 mg
	Second	Discontinue Drug	Discontinue Drug	Discontinue Drug
Grade 3 or 4 cardiac failure Grade 4 cardiac arrhythmias	First	Discontinue Drug	Discontinue Drug	Discontinue Drug

¹Evaluate the risk-benefit before resuming ibrutinib treatment

²If clinically indicated, the use of anticoagulants or antiplatelet agents may be considered for thromboprophylaxis of atrial fibrillation.

5.1.1.6. Dose Modification for Hepatic Impairment

Dose modifications for hepatic impairment will depend on total bilirubin level and subsequent changes in bilirubin levels per Table 3 below. If the elevation of bilirubin is due to a non-hepatic cause or Gilbert's Syndrome, then no dose modifications are necessary. Ibrutinib is metabolized in the liver and therefore subjects with clinically significant chronic hepatic impairment at the time of Screening (Child- Pugh class C) are excluded from study participation. Refer to Appendix D for Child-Pugh classification. Please refer to Table 3 for dose modifications due to hepatic impairment. Subjects who develop acute hepatic toxicity with liver enzymes Grade 3 or higher while on study should be managed per standard dose modification guidelines for unmanageable Grade 3 toxicity in Section 5.1.1.4.

Table 4. Dose Modification Guidance for Hepatic Impaired Subjects

Starting Dose Level by Bilirubin Levels	Bili \leq 1.5 x ULN at baseline 420 mg	Bili $>$ 1.5-3 x ULN at baseline 140 mg
On-study Bili \leq 1.5 x ULN	Continue 420 mg	Increase to 420 mg
On-study Bili $>$ 1.5-3 x ULN	Reduce to 140 mg	Continue 140 mg
On-study Bili $>$ 3 x ULN	Hold until Bili $>$ 1.5-3 x ULN, then restart 140 mg When bili level \leq 1.5 x ULN restart at 420mg	Hold until Bili $>$ 1.5-3 x ULN, then restart 140 mg When bili level \leq 1.5 x ULN restart at 420mg

In the event a patient has had a dose reduction due to a non-hepatic toxicity and then develops elevated bilirubin (or vice versa) that requires a dose reduction, the lower of the two dose reductions should be used.

5.1.1.7. Dose Modification for Concomitant Use of CYP3A Inhibitors

Dose adjustment of ibrutinib secondary to concomitant use of CYP 3A4 inhibitors should follow Table 4. Concomitant use of strong CYP inhibitors is not permitted in subjects with chronic hepatic impairment.

Table 5. Dose Modification Guidance for CYP3A4 Inhibitors

Co-administered Drug	Recommended Ibrutinib Dose for the Duration of the Inhibitor Use
Mild CYP3A4 inhibitors	420 mg once daily. No dose adjustment required.
Moderate CYP3A4 inhibitors	420 mg once daily. No dose adjustment required.
Voriconazole Posaconazole at doses less than or equal to suspension 200 mg BID or delayed-release tablet 300mg QD	280 mg once daily.
Posaconazole at higher doses	140 mg once daily.
Other strong CYP3A4 inhibitors	Avoid concomitant use. If these inhibitors will be used short term (such as anti-infectives for seven days or less), interrupt IMBRUVICA.

After discontinuation of a CYP3A4 inhibitor, resume previous dose of ibrutinib.

If Bili $>$ 1.5 x ULN, avoid and/or discontinue voriconazole, posaconazole, or other strong CYP3A4 inhibitor.

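### When an azole is stopped because bilirubin has risen, Sections 5.1.1.6 and 5.1.1.7 give conflicting ibrutinib doses, and nothing says which governs

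*Combined protocol and SAP*

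**What the plan says.** Several rules in the protocol set the ibrutinib dose. Three matter here.

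- **CYP3A inhibitors (Section 5.1.1.7, Table 5).** The dose is 280 mg with voriconazole or lower-dose posaconazole and 140 mg with higher-dose posaconazole, for as long as the inhibitor is taken. Afterwards: "After discontinuation of a CYP3A4 inhibitor, resume previous dose of ibrutinib". The next sentence applies when bilirubin exceeds 1.5 x ULN and says to "avoid and/or discontinue voriconazole, posaconazole, or other strong CYP3A4 inhibitor". It names no ibrutinib dose.
- **Bilirubin (Section 5.1.1.6, Table 4).** For a patient whose baseline bilirubin was at most 1.5 x ULN, an on-study value above 1.5 and up to 3 x ULN carries the entry "Reduce to 140 mg". Above 3 x ULN the drug is held. Elevations of non-hepatic origin or from Gilbert's Syndrome are exempt.
- **Non-cardiac toxicity (Section 5.1.1.4).** After a reduction, the dose may be "re-escalated after 4 weeks of a dose reduction in the absence of a recurrence of the toxicity that led to the reduction".

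One sentence, at the end of Section 5.1.1.6, deals with two reasons arising together. It begins "In the event a patient has had a dose reduction due to a non-hepatic toxicity and then develops elevated bilirubin (or vice versa" and tells the investigator to use the lower of the two reductions. It does not mention CYP3A inhibitors.

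**The concern.** The two closing sentences of Section 5.1.1.7 chain together. Raised bilirubin triggers stopping the azole, and stopping the azole triggers a return to the earlier ibrutinib dose. At the same moment the bilirubin table in the preceding section calls for a reduced dose or a hold. One laboratory result therefore sets off two written instructions that point in opposite directions.

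The sequence is foreseeable from the protocol's own text. Section 5.1.1.2 says: "It is expected that many subjects commencing therapy for cGVHD will require anti-fungal prophylaxis". The exclusion criteria expressly allow voriconazole and posaconazole. Inclusion criterion 7 admits bilirubin up to 3 x ULN when due to cGVHD, and liver is a scored cGVHD organ in Appendices E and G.

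At stake is the dose of the investigational drug in a patient with a liver signal. So is the consistency of exposure behind the trial's estimate of related grade 3 or higher adverse events.

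**Working it through.** There is no planned figure to reproduce and no sample-size formula is involved. The check is to follow one patient through the rules as written.

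**Inputs**

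| Input | Value | Source |
|---|---|---|
| Standard dose | 420 mg daily | Section 5.1.1.2 |
| Dose on voriconazole | 280 mg | Table 5 |
| Dose once the inhibitor stops | the earlier dose, no bilirubin condition | Section 5.1.1.7 |
| Action on the azole at bilirubin > 1.5 x ULN | avoid or stop | Section 5.1.1.7 |
| Ibrutinib at bilirubin > 1.5-3 x ULN | 140 mg | Table 4 |
| Ibrutinib at bilirubin > 3 x ULN | hold | Table 4 |

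**Sequence**

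1. Baseline bilirubin is at most 1.5 x ULN, so the patient starts at 420 mg.
2. Voriconazole is added: 280 mg.
3. Bilirubin rises above 1.5 x ULN for a hepatic reason, and the azole is stopped.
4. The ibrutinib dose is then:

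| On-study bilirubin | Section 5.1.1.7 (resume) | Table 4 | Difference |
|---|---|---|---|
| > 1.5-3 x ULN | 420 mg | 140 mg | 420/140 = 3.0-fold |
| > 3 x ULN | 420 mg | hold | 420 mg against none |

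From the 280 mg being taken, one instruction raises the dose by half (420/280 = 1.5) and the other halves it (140/280 = 0.5). With higher-dose posaconazole the patient is at 140 mg before the azole stops. The resume sentence then gives 420 mg and Table 4 gives 140 mg, again 3.0-fold.

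**Is there a tie-breaker?**

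- The combining sentence in Section 5.1.1.6 needs a reduction for a non-hepatic toxicity. A dose set because of a co-administered drug is not a toxicity reduction, so the sentence does not reach this pair.
- Tables 2 and 3 have columns for 420, 280 and 140 mg starting doses. They link toxicity to a lower starting dose, but do not link bilirubin to CYP3A inhibitors.
- The Synopsis, Section 3.1, Section 6.2.1 and Appendix A say that adjustment is needed for inhibitors or hepatic impairment, or point to the tables. None ranks the two.
- Section 5.1.1.7 bars strong inhibitors in chronic hepatic impairment. That does not settle an on-study rise in a patient already on an azole.

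**Is it only table numbering?** No. Section 5.1.1.7 does send the reader to Table 4 for inhibitor dosing, although that is the bilirubin table, and Section 5.1.1.6 cites Table 3, which is the cardiac table. Correcting every reference leaves the conflict in place.

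**The term *previous dose*.** It is undefined for a patient already on an azole at Day 1, who never took another dose. It is unclear for a patient reduced for toxicity while on an azole: the resume sentence carries no condition, whereas Section 5.1.1.4 makes re-escalation depend on 4 weeks without recurrence.

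**The case against.** The best reply is that the resume sentence belongs to the CYP3A section and lifts only the CYP3A adjustment. Table 4 is keyed to current bilirubin and goes on applying, so a careful clinician reaches one dose. That is a reasonable reading, and a dose increase after a liver signal would happen only if Table 4's explicit entry were overlooked. But the documents do not state this precedence. Section 5.1.1.6 also shows that its authors thought a written combining rule was needed for another pair of reasons.

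Three stronger readings are tempting, and the documents do not support them.

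- **That Tables 4 and 5 also contradict each other when bilirubin is normal.** A reader might set Table 4's "Increase to 420 mg" against the 280 or 140 mg in Table 5. Table 5, however, governs for the period of inhibitor use, and the Synopsis, Section 3.1 and Appendix A require adjustment with these azoles. If the 420 mg entries in Table 4 were true rivals, the azole rows of Table 5 would have no effect in any patient with normal bilirubin. Counting cells where the two tables differ overstates the problem for the same reason, and because it includes azole use at raised bilirubin, which Section 5.1.1.7 tells the investigator to avoid.
- **That stopping an azole cancels a toxicity reduction.** The text does not say so, and the re-escalation condition in Section 5.1.1.4 remains in force. Likewise, the dose for a patient who entered on an azole can probably be worked out from the standard dose and Table 4. Both are unclear wording, not conflicting instructions.
- **That sites will dose differently.** There is one centre.

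**Conclusion.** The conflict is real and specific. When an azole is stopped because bilirubin has risen, Section 5.1.1.7 read literally gives 420 mg. Table 4 gives 140 mg above 1.5 and up to 3 x ULN, and a hold above 3 x ULN. The difference is 3-fold, or full dose against none, and no stated rule decides between them.

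This rests on four assumptions: the patient took 420 mg before the azole, had no intervening toxicity reduction, has a bilirubin rise that is neither non-hepatic nor due to Gilbert's Syndrome, and actually has the azole stopped. The undefined *previous dose* is a secondary wording point.

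The documents give no figure for how many of the 35 patients would meet this sequence, so no effect on the efficacy or safety results can be claimed. The supported consequence is that treating clinicians at the centre could dose the same patient differently while each follows the text. Because the contradiction concerns the study drug in a patient with raised bilirubin and is cheap to remove, it should be corrected. Nothing here implies which dose is right.

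**What to change.** Amend Sections 5.1.1.4 to 5.1.1.7 so that they can be read together:

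1. State which instruction governs when a CYP3A-driven dose and a bilirubin- or toxicity-driven dose apply at once, including at the moment an inhibitor is stopped.
2. Make the resume sentence in Section 5.1.1.7 expressly subject to that statement.
3. Define *previous dose*, covering patients who entered on an azole and patients reduced for toxicity while taking one.

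The sponsor's medical lead decides which dose governs. Simply widening the existing combining sentence to every reason would itself choose a clinical rule, so it should not be done by default. The table cross-references in these sections can be corrected in the same amendment.

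The cost is a few sentences of protocol text, with no new procedures, visits or patients.
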